1.2.5.2. Immunogenicity Parameters

The primary immunogenicity endpoints are as follows:

- Geometric mean titers (GMT) of Marburg GP protein-specific IgG antibody as measured by ELISA on Days 1 and 29
- GMT of PsVNT₅₀ and PsVNT₈₀ MARV GP-specific neutralizing antibody titers (the reciprocals of the serum dilutions at which 50% and 80% of the input pseudovirion was neutralized, respectively) as measured by Pseudovirion neutralization assay (PsVNA) on Days 1 and 29

If the corresponding titer value is below the lower limit of quantitation (LLOQ), the titer value will be considered as LLOQ/2 at such visit for GMT computation. For ELISA titers below limit of detection (LOD), the titer will be assigned a value of 1 ELISA unit/mL for GMT computations.

Secondary immunogenicity endpoints include the following:

- GMT Marburg GP protein-specific IgG ELISA antibody on all other study days through Day 181
- GMT PsVNT₅₀ and PsVNT₈₀ on all other study days to Day 181
- Seroconversion rate defined as at least 4-fold increase in Marburg GP-specific IgG (ELISA) titer compared to Day 1 for subjects with baseline titers > LLOQ. Otherwise, if baseline titer < LLOQ or <LOD, seroconversion is defined as at least 4-fold increase over LLOQ/2.
- Seroconversion rate defined as at least 4-fold increase in Marburg GP-specific neutralizing antibody titer PsVNA compared to Day 1 for subjects with baseline titers > LLOQ.

Otherwise, if baseline titer < LLOQ, seroconversion is defined as at least 4-fold increase over LLOQ/2.

- Geometric mean fold increase in Marburg GP-specific IgG (ELISA)
- Geometric mean fold increase in Marburg GP-specific neutralizing antibody titer (PsVNA)
- Seroresponse rate defined as at least 2-fold increase in Marburg GP-specific IgG (ELISA) compared to Day 1 for subjects with baseline titers > LLOQ. Otherwise, if baseline titer < LLOQ or <LOD, seroresponse is defined as at least 2-fold increase over LLOQ/2.
- Seroresponse rate defined as at least 2-fold increase in Marburg GP-specific neutralizing antibody titer PsVNA compared to Day 1 for subjects with baseline titers > LLOQ.
 Otherwise, if baseline titer < LLOQ, seroresponse is defined as at least 2-fold increase over LLOQ/2.
- Reverse cumulative distribution of titers (IgG ELISA and PsVNA)
- The correlation between the IgG ELISA and neutralizing antibody titers on all study days tested
- The correlation between blood viremia AUC and IgG ELISA and neutralizing antibody

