3. GENERAL STATISTICAL METHODS

3.1. Sample Size Justification

The sample size for this Phase 1 study (N=36 subjects; total N=10 per vaccine dose level [30 vaccinees and 6 placebo]) was selected to provide initial data and obtain estimates of safety and immunogenicity parameters and their respective variabilities. Group size is based on prior experience with ERVEBO safety studies and assumptions from the responses seen in the preclinical studies. This Phase I study is therefore designed with the goal of providing further information for better planning of future in-human studies. As this is a FIH study of PHV01, the sample size was established to provide reasonable information for descriptive purposes and not specifically designed for formal hypothesis testing.

Safety: With a sample size of 10 subjects, an upper bound of 30.9% is established for the 2-sided 95% confidence interval (CI) for the incidence of an AE in the case that the event is not observed according to the two-sided 95% (Clopper-Pearson) exact CI. Alternatively, when pooled together all 30 vaccinees, an upper bound of 11.6% is provided. This established the sample sizes needed to ensure minimal AE rates could be detected with confidence.

Immunogenicity: Clinical data for the rVSV-ZEBOV-GP Ebola vaccine showed that a dose of 3×10^6 pfu/mL yielded a Day 29 GMT IgG ELISA titer of 1400 EU/mL and geometric standard deviation (SD) of 3.3. Assuming that the variability in responses to PHV01 is similar, the proposed group sizes afford 80% (alternate 90%) power to detect a 6.4-fold (alternate 8.6-fold) increase, comparing geometric mean ELISA titer using a two-sided test with alpha=0.05 for each vaccine group with the placebo group. Alternatively, performing the same comparison against placebo by pooling all three treatment groups with a total 30 vaccinated subjects, we would have 4.7-fold and an alternate 5.9-fold with 80% and 90% power, respectively.

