3.10. Missing, Unused, and Spurious Data

In general, there will be no substitutions made to accommodate missing data points. All data recorded on the case report form will be included in data listings that will accompany the CSR.

Subjects with negative post-baseline antibody response (defined as the corresponding titers < LLOQ) will have a titer value assigned as LLOQ/2.

When tabulating AE data, partial dates will be handled as follows. If the day of the month is missing, the onset day will be set to the first day of the month unless it is the same month and year as study treatment. In this case, in order to conservatively report the event as treatment-emergent, the onset date will be assumed to be the date of treatment. If the onset day and month are both missing, the day and month will be assumed to be January 1, unless the event occurred in the same year as the study treatment. In this case, the event onset will be coded to the day of treatment in order to conservatively report the event as treatment-emergent. A missing onset date will be coded as the day of treatment.

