4.3. Immunogenicity Evaluation

Immunogenicity analyses will be conducted using the PP population. Supportive analyses of immunogenicity will be based on the mITT population if the number of subjects excluded from PP population is more than 10%.

4.3.1. Geometric Mean Titers and Mean Fold Increase of IgG ELISA Antibody and Neutralizing Antibody PsVNT

For IgG ELISA antibody titers and neutralizing antibody titers PsVNT (PsVNT₅₀ and PsVNT₈₀), GMT, and 95% confidence limit will be provided on Days 1, 8 (if tested), 15, 29, 85, and 181, where the GMT is calculated as the anti-log of the base-2 log transformed mean and the same for the corresponding confidence limit. Results will be presented by treatment group along with a combined PHV01 group, and the descriptive statistics will include the GMT, the geometric standard deviation, 25th percentile, median, 75th percentile, minimum, and maximum values. If appropriate, the analyses will be repeated for the GMT using the anti-log of the base-10 log transformed mean.

Pairwise comparison of the above antibody titer levels for each PHV01 dose level to one another and to the placebo group, as well as the comparison of the combined PHV01 dose group relative to the placebo group will be performed with Satterthwaite t-tests. T-tests will be performed on log-2 transformed values and the resulting estimated mean difference and associated 95% CI will then be back transformed using base-2 antilogarithms to obtain estimates

on the ratio scale. If appropriate, the analyses will be repeated using base-10 log transformed values and back transformed using base-10 antilogarithms to obtain estimates. In the event of extreme outliers or non normally distributed data, Wilcoxon rank-sum test may be performed to support the comparison.

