Additionally, Analysis of Variance (ANOVA) models will be used to compare each PHV01 dose level to one another and to placebo for Days 8 (if tested), 15, 29, 85 and 181. The response variable will be the log-2 transformed ELISA titer values for the time point under consideration. If there is a significant difference between the GMTs, i.e., where the p-value from the F-test is < 0.05, then post-hoc pairwise tests using Tukey's method will be used to compare each dose with one another and each dose with placebo. The estimated mean differences on the log-2 scale between the treatment groups will be expressed as the ratio of GMTs. The base-2 antilogarithm of each mean difference represents the GMT ratio and the base-2 antilogarithms of the 95% CI limits for the mean difference represent the confidence limits for the GMT ratio.

Similarly, the mean fold increase of ELISA titers and PsVNT will be calculated by subtracting the base-2 log transformed values at baseline (Day 1) from the respective study day (Day 8 [if tested], 15, 29, 85, 181) for each subject and averaged within treatment group. If baseline titer value is <LLOQ or <LOD (ELISA only), baseline will be assigned as LLOQ/2 for purposes of deriving fold increase. The results will be presented by transforming back the anti-log. The 95% CI will be calculated based on the inverse of the log2 transformed fold increase values from the t-distribution. Results will be presented for each study day (Day 8 [if tested], 15, 29, 85, 181) by treatment group along with a combined PHV01 group, and the descriptive statistics will include the geometric mean fold-increase from baseline, the geometric standard deviation, 25th percentile, median, 75th percentile, minimum, and maximum values.

Pairwise ratios of the geometric mean fold rise and the associated 95% confidence intervals will be estimated for each PHV01 dose group relative to one another and to the placebo group, as well as the ratio of the combined PHV01 dose group relative to the placebo group on Days 8 (if tested), 15, 29, 85, and 181. Pairwise comparisons will be performed using Satterthwaite's t-test. T-tests will be performed on log-2 transformed values of the individual fold-rise values. The resulting estimated mean difference and associated 95% CI will then be back transformed using base-2 antilogarithms to obtain estimates on the ratio scale.

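### The additional ELISA ANOVA in SAP 4.3.1 pools one variance over the PHV01 and placebo groups, so its intervals are correctly scaled only if placebo titers happen to vary as much as vaccine titers

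*SAP*

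**What the plan says.** SAP 4.3.1 compares log-2 titers between every pair of doses, each dose and placebo, and the combined PHV01 group and placebo. It says these comparisons "relative to the placebo group will be performed with Satterthwaite t-tests", which allow each group its own variance.

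It then adds, for ELISA titers only: "Analysis of Variance (ANOVA) models will be used to compare each PHV01 dose level to one another and to placebo". If the overall F-test has p < 0.05, Tukey's method is applied to all dose-dose and dose-placebo pairs. No unequal-variance version is mentioned, and the SAP does not say which of the two analyses governs.

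Two rules set the value of low titers:

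- SAP 1.2.5.2 assigns LLOQ/2 below the LLOQ, with a separate ELISA rule: "For ELISA titers below limit of detection (LOD), the titer will be assigned a value of 1 ELISA unit/mL for GMT computations".
- SAP 3.10 says that post-baseline titers below the LLOQ "will have a titer value assigned as LLOQ/2", with no separate value below the LOD.

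SAP 3.1 gives the group sizes ("total N=10 per vaccine dose level [30 vaccinees and 6 placebo") and takes its variability from an Ebola vaccine study that "yielded a Day 29 GMT IgG ELISA titer of 1400 EU/mL and geometric standard deviation (SD) of 3.3". Protocol 4.5 (criterion 14) excludes people with prior VSV infection, a VSV-vectored or filovirus vaccine, or possible filovirus contact.

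**The concern.** A standard one-way ANOVA estimates one residual variance from all four groups. Given the exclusions, most placebo sera should be negative and so carry substituted values, while the vaccine groups are assumed to have a geometric SD of 3.3. There is no reason to expect the placebo variance to match.

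When it does not match, the pooled variance is wrong for every contrast. The error is largest for dose against placebo, because the misjudged placebo variance is divided by only 6. The dose-dose contrasts are affected as well: placebo floor values enter the error term for comparisons in which placebo plays no part.

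The report would then show two sets of intervals for the same ELISA contrasts, built on incompatible variance assumptions, with nothing to say which one to read.

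The gate is a separate weakness. The F-test includes placebo, so an immunogenic vaccine passes it even when the doses are identical.

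**Working it through.** **Inputs.** Group sizes 10, 10, 10 and 6; geometric SD 3.3; two-sided alpha 0.05 (all SAP 3.1). On the log-2 scale the vaccine SD is log2(3.3) = 1.722. The placebo SD, LOD and LLOQ are not given. Write r for placebo SD divided by vaccine SD, and treat r as an assumption.

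**The plan's own figure.** SAP 3.1 claims "80% (alternate 90%) power to detect a 6.4-fold (alternate 8.6-fold) increase", "using a two-sided test with alpha=0.05 for each vaccine group with the placebo group". An equal-variance t-test with 10 against 6 (14 df) and SD ln(3.3) gives 79.9% power at 6.4-fold and 90.0% at 8.6-fold. The figures reproduce, and they rest on r = 1.

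**Formulas**, in units of the vaccine SD:

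- Pooled variance = (27 + 5r²)/32
- Dose-placebo SE: ANOVA √[pooled variance × (1/10 + 1/6)]; correct √(1/10 + r²/6)
- Dose-dose SE: ANOVA √(pooled variance × 2/10); correct √(2/10)

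**Placebo constant (r = 0).** Pooled variance = 27/32 = 0.844.

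- Dose-placebo SE = √(0.844 × 0.2667) = 0.474, against √0.1 = 0.316: ratio 1.50.
- Dose-dose SE = √(0.844 × 0.2) = 0.411, against 0.447: ratio 0.92.

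**Interval widths at r = 0.** The Tukey multiplier is 2.709 (four groups, 32 df), the unadjusted t is 2.037 (32 df), and the Satterthwaite t is 2.262 (9 df) for dose-placebo and 2.101 (18 df) for dose-dose.

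- Dose-placebo: Tukey 2.709 × 0.474 = 1.285; Satterthwaite 2.262 × 0.316 = 0.715; ratio 1.80. This splits into 1.35 from pooling (unadjusted ANOVA against Satterthwaite) and 2.709/2.037 = 1.33 from the Tukey multiplier.
- Dose-dose: Tukey 2.709 × 0.411 = 1.113; Satterthwaite 2.101 × 0.447 = 0.940; ratio 1.18. The Tukey interval is the wider one.

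**Is r near zero?** Suppose five placebo sera are below the LOD (1 unit, log2 = 0) and one lies between LOD and LLOQ (LLOQ/2). The placebo SD is then log2(LLOQ/2) × √(1/6). The LLOQ values below are assumed, and the SE ratios are ANOVA divided by correct.

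| Assumed LLOQ | Placebo SD (log-2) | r | Dose-placebo SE ratio | Dose-dose SE ratio |
|---|---|---|---|---|
| 10 | 0.95 | 0.55 | 1.26 | 0.94 |
| 20 | 1.36 | 0.79 | 1.11 | 0.97 |
| 50 | 1.90 | 1.10 | 0.96 | 1.02 |
| 100 | 2.30 | 1.34 | 0.87 | 1.06 |

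One serum out of six is enough to move the result from clearly too wide to too narrow.

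**Simulation** (100,000 trials, normal log titers, three identical doses 20-fold above placebo):

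| r | Dose-placebo coverage, unadjusted ANOVA | Dose-placebo coverage, Tukey | Familywise error over three dose pairs, planned Tukey | Same, Tukey on PHV01 groups only (27 df) | F-test passes |
|---|---|---|---|---|---|
| 0 | 99.5% | 99.9% | 5.0% | 5.1% | 100% |
| 0.55 | 98.4% | 99.8% | 4.1% | 5.0% | 100% |
| 1 | 95.0% | 98.9% | 2.8% | 4.9% | 99.7% |
| 1.34 | 91.4% | 97.5% | 1.9% | 5.0% | 98.0% |

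At r = 0 a separate run of 40,000 trials gave Satterthwaite dose-placebo coverage of 95.2%. The planned dose-dose error rate drifts with the placebo variance; the PHV01-only version does not. The F-test passes in at least 98% of trials although the doses do not differ.

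**The case against.** The strongest case on the other side is that little depends on this ANOVA. It is additional and ELISA-only. Every contrast already has a Satterthwaite test, with a Wilcoxon test available for outliers or non-normal data. That stands, and it limits the consequence.

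Three stronger readings are tempting, and the documents do not support them.

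- *A reader might infer that the SAP's rules make placebo titers constant.* That follows only if all six sera fall on the same side of the LOD, or if SAP 3.10 overrides SAP 1.2.5.2. With two floor values the direction of the error can reverse.
- *A reader might infer that dose-dose comparisons produce too many false positives.* The standard error is too small at r = 0, but Tukey over four groups more than covers it per contrast (error 1.9%), and familywise error over the three dose pairs stays near 5% or lower. Measured against the SAP's Satterthwaite intervals, the Tukey dose-dose intervals are 18% wider.
- *A reader might infer that Phase 2 dose selection rests on these intervals.* Protocol 7.2 bases the dose-guiding interim analysis on descriptive statistics by dose group together with safety, and SAP 3.7 relies on combined statistical and clinical judgement. No section ties the choice to the ANOVA.

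It is also fair that a gate which nearly always opens does no harm to Tukey's error control. The complaint is only that the gate tells the reader nothing about dose. Finally, with a 20-fold response and constant placebo, the Tukey dose-placebo intervals still exclude 1 in 99.97% of trials, so that conclusion would not change.

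**Conclusion.** The concern holds in conditional form. The ANOVA and Tukey step applies one variance to groups that the plan gives no reason to think share one, alongside tests in the same section that avoid this assumption. Its standard errors are right only at r = 1.

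If placebo is constant, the dose-placebo SE is 1.50 times the correct value, Tukey intervals are 1.80 times the Satterthwaite width (about half of that gap, on a multiplicative scale, is the Tukey multiplier), and the dose-dose SE is 8% too small. With one placebo serum between the floors and an assumed LLOQ of 10 to 100, the dose-placebo ratio runs from 1.26 down to 0.87. These figures assume equal variance across the three doses and a geometric SD of 3.3; the ratios at a given r do not depend on the 3.3.

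The gate finding depends much less on r: the F-test mostly reflects the vaccine-placebo difference. The matter is worth correcting because the correction is cheap, not because a trial conclusion is shown to be at risk.

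**What to change.** In SAP 4.3.1:

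1. Run the ANOVA and Tukey dose-dose comparisons on the three PHV01 groups only (27 df). If variances may also differ between doses, for example because low-dose non-responders sit at the floor, use Games-Howell instead.
2. Leave every placebo contrast to the Satterthwaite tests already planned, and say that these govern.
3. Drop the placebo-inclusive F-test as a condition for dose comparisons.
4. Reconcile the below-LOD value in SAP 1.2.5.2 with the LLOQ/2 rule in SAP 3.10, and state the LOD and LLOQ.

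Do not replace the ANOVA with a separate-variance mixed model that includes placebo. If placebo titers are constant, their estimated variance is zero and the model breaks down.

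The cost is SAP wording and a small programming change. The dose contrasts have 27 rather than 32 df, but the Tukey multiplier falls from 2.709 (four groups) to 2.479 (three groups). At r = 0 the interval half-width is 2.479 × 0.447 = 1.109 vaccine SDs against 1.113 now, so practically no precision is lost.

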4.3.2. Seroconversion Rate and Distribution of ELISA Titers and PsVNT

Seroconversion is defined as at least 4-fold increase in the titer when compared to baseline (Day 1). If the baseline titer is <LLOQ or <LOD (ELISA only), the baseline value used to determine seroconversion will be assigned as LLOQ/2. In these cases, seroconversion occurs if the fold-increase at post-baseline visit is greater than or equal to 4 times the LLOQ/2.

The seroconversion rate of ELISA titers and PsVNT and their exact 95% CIs based on the Clopper-Pearson method will be presented by treatment group and combined PHV01 group on Days 8 (if tested), 15, 29, 85, 181. The comparison between each of the PHV01 vaccine dose levels, the combined PHV01 vaccine group, and the placebo arm will also be performed. Comparisons will be based on the 95% CI for differences in seroconversion rate and will use the Newcombe score method. The analysis will be repeated separately for males and females. These

differences will be used to indicate possible dose-related responses. A difference in seroconversion rate between a given PHV01 dose group and placebo that is greater than zero (i.e., if the lower bound of the 95% CI for difference in seroconversion rate is greater than zero) indicates the rate of seroconversion in the PHV01 dose group is larger than the rate in the placebo group.

Reverse cumulative distribution curves of ELISA titers and PsVNT will be generated by treatment group on Days 8 (if tested), 15, 29, 85, 181 respectively, where the x-axis will be the observed log-2 transformed titers and the y-axis will be the percentage of subjects having a log-2 transformed titer greater than or equal to each of the observed log-2 transformed titers on the x-axis.

Boxplots by study day and treatment group will present the mean, median, interquartile range, and 95% CI for the ELISA titers and PsVNT levels on the log-2 scale and will be overlaid with jittered dots representing individual datapoints. Spaghetti plots will also be plotted for ELISA titers and PsVNT levels on log-2 scale by days since dosing, treatment group and subject. Line plots will present GMTs for ELISA titers and PsVNT50 levels at each visit by treatment group.

Exploratory endpoints to examine aspects of both cell mediated and humoral immunity will be collected but not analyzed.

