4.5. SUBJECT EXCLUSION CRITERIA

- 1. Presence of objective, measured fever >100.4°F/38°C or acute illness within 1 week before study product injection
- 2. Inability to observe possible local reactions at the eligible injection site (either deltoid region), which is unacceptably obscured due to a physical condition or permanent body art, in the opinion of the Investigator
- 3. Has BMI of 35 or greater
- 4. Have an active malignancy or history of metastatic or hematologic malignancy
- 5. Subjects with atopic dermatitis (eczema), recurrent oral/mucosal vesicles, or ulcerative lesions
- 6. Subjects with a history of chronic inflammatory disease (e.g., rheumatoid arthritis, psoriatic arthritis, reactive arthritis, ankylosing spondylitis, systemic lupus erythematosus, psoriasis, Crohn's disease, ulcerative colitis, and gout), symptomatic osteoarthritis, or any other autoimmune or autoinflammatory disorder
- 7. History of severe local or systemic reactions to any vaccination or a history of severe allergic reactions
- 8. Known allergy to the excipients of the PHV01 vaccine product (Tris buffer, recombinant human albumin)
- 9. Any chronic or active neurologic disorder, including seizures and epilepsy (excluding a single febrile seizure as a child), or history of Guillain-Barré Syndrome
- 10. Receipt of investigational product up to 30 days prior to randomization
- 11. Receipt of licensed or authorized non-live vaccines within 14 days of planned study immunization (30 days for live vaccines)
- 12. Administration of IgGs and/or any blood products within the 120 days preceding study entry or planned administration during the 6-month study period
- 13. Administration of systemic chronic immunosuppressants (defined as more than 14 days) or other immune modifying drugs within 6 months of study entry
- 14. History of prior infection with VSV, receipt of a VSV vectored or filovirus vaccine, or employment or activity that involves potential contact with Marburgvirus or other Filoviruses

- 15. History of blood donation within 60 days of enrollment or plans to donate within the study period
- 16. Any baseline laboratory screening tests that, in the opinion of the Investigator, are considered clinically significant
- 17. Any serologic evidence of acute or chronic hepatitis B or C infection (unless HCV RNA RT-qPCR is negative)

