4.3.3. Seroresponse Rate of ELISA Titers and PsVNT

Seroresponse is defined as a \geq 2-fold increase in the titer when compared to baseline (Day 1). If the baseline titer is <LLOQ or <LOD (ELISA only), a seroresponse is defined as titer greater than or equal to LLOQ.

The number, percent, and associated exact 95% CI of subjects whose baseline response is negative, i.e., less than the LLOQ, will be tabulated for each treatment group and the combined PHV01 vaccine group.

The number, percent, and exact 95% CI of seroresponse for Days 8 (if tested), 15, 29, 85 and 181 will be calculated. Comparisons between each PHV01 dose level with one another and with the placebo group will be performed using the Newcombe method.

Analyses of seroresponse rates will be performed separately for the ELISA IgG and neutralizing antibody titers.

4.3.4. Correlation between IgG ELISA and neutralizing antibody titers on Days 29, 85 and 181

Spearman's rank correlation will be used to estimate the association between IgG antibody titers and PsVNA titers for each PHV01 vaccine dose group including the combined PHV01 group at Days 29, 85, and 181.

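### SAP 4.3.2 gives two seroconversion thresholds for subjects with a baseline below LLOQ: 2 × LLOQ from its first two sentences and, read literally, LLOQ² from its third

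*SAP*

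**What the plan says.** SAP 4.3.2 handles seroconversion in three steps.

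1. It defines seroconversion as a rise in titer of at least 4-fold over the Day 1 value.
2. For a baseline below LLOQ (or, for ELISA, below LOD), "the baseline value used to determine seroconversion will be assigned as LLOQ/2".
3. It adds: "In these cases, seroconversion occurs if the fold-increase at post-baseline visit is greater than or equal to 4 times the LLOQ/2".

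SAP 1.2.5.2 defines the same endpoint. For ELISA: "Otherwise, if baseline titer < LLOQ or <LOD, seroconversion is defined as at least 4-fold increase over LLOQ/2". For PsVNA: "Otherwise, if baseline titer < LLOQ, seroconversion is defined as at least 4-fold increase over LLOQ/2".

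Two neighbouring rules show the scale intended. SAP 4.3.1 derives fold increase from the same substituted baseline: "If baseline titer value is <LLOQ or <LOD (ELISA only), baseline will be assigned as LLOQ/2 for purposes of deriving fold increase". SAP 4.3.3 states the parallel 2-fold rule for low baselines directly as a titer: "a seroresponse is defined as titer greater than or equal to LLOQ".

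Protocol 7.2 lists seroconversion by ELISA and PsVNA among the Day 29 interim outputs, and says the interim analysis is to guide dose selection for Phase 2. Neither document states an LLOQ for either assay.

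**The concern.** The third sentence of SAP 4.3.2 compares a ratio (the fold-increase) with a titer (4 × LLOQ/2). LLOQ/2 therefore enters twice: once as the divisor that produces the fold-increase, and again in the cutoff. A programmer who codes that sentence gets a different responder definition from one who codes the two sentences before it, or SAP 1.2.5.2.

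For any LLOQ above 2 the literal rule is the stricter one, so some subjects with a genuine 4-fold rise would be counted as non-responders. The distortion depends on the LLOQ, so it would differ between ELISA and PsVNA if their LLOQs differ. SAP 4.3.2 uses differences in seroconversion rate to indicate possible dose-related responses, and reads a Newcombe lower limit above zero as a higher rate than placebo. A misapplied threshold would feed straight into those statements.

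The branch probably covers most subjects. Exclusion 14 in Protocol 4.5 rules out prior VSV infection and "receipt of a VSV vectored or filovirus vaccine, or employment or activity that involves potential contact with Marburgvirus or other Filoviruses", so most baselines should be below LLOQ.

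**Working it through.** **Thresholds.** Write L for LLOQ and T for the post-baseline titer. With the baseline set to L/2 (SAP 4.3.1 and 4.3.2), fold-increase = T/(L/2).

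- SAP 4.3.2, first two sentences: T/(L/2) ≥ 4, so T ≥ 2L.
- SAP 1.2.5.2, both assays: at least 4-fold over L/2, so T ≥ 4 × L/2 = 2L.
- SAP 4.3.2, third sentence read literally: T/(L/2) ≥ 4 × L/2, so T ≥ 4 × (L/2)² = L².

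The ratio of the literal to the intended threshold is L²/(2L) = L/2. It equals 1 only at L = 2. Below that the literal rule is laxer, and above it stricter.

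**Size.** No figure stated in the plan depends on this rule, so there is none to reproduce for it. An illustration needs a titer distribution and an LLOQ.

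- Spread: geometric SD 3.3, which the sample-size sections (Protocol 7.1, SAP 3.1) carry over from the Ebola vaccine. As a check, a two-sample t-test on the log scale with SD ln 3.3 = 1.194 and two-sided 5% alpha reproduces the plan's power statements. For 10 v 6 it gives 79.9% at 6.4-fold and 90.0% at 8.6-fold. For 30 v 6 it gives 80.4% at 4.7-fold and 89.8% at 5.9-fold.
- Location: GMT 1400 EU/mL. This is my assumption. The plan reports it for the Ebola vaccine at 3 × 10⁶ pfu/mL and does not assume it for PHV01.
- LLOQ: assumed from 2 to 100, because none is given.

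Formula: P(T ≥ t) = 1 − Φ[(ln t − ln 1400)/ln 3.3].

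Worked at L = 50:
- t = 100: (4.605 − 7.244)/1.194 = −2.21, giving 98.6%.
- t = 2500: (7.824 − 7.244)/1.194 = 0.486, giving 31.4%.

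| LLOQ (assumed) | 2 × LLOQ | LLOQ² | Ratio | Expected rate, 2 × LLOQ | Expected rate, LLOQ² |
|---|---|---|---|---|---|
| 2 | 4 | 4 | 1 | about 100% | about 100% |
| 10 | 20 | 100 | 5 | 99.98% | 98.6% |
| 20 | 40 | 400 | 10 | 99.9% | 85.3% |
| 50 | 100 | 2,500 | 25 | 98.6% | 31.4% |
| 100 | 200 | 10,000 | 50 | 94.8% | 5.0% |

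**Effect on the planned comparison at LLOQ 50.** In a group of 10 the expected counts are about 10 and about 3. Take 0 of 6 on placebo (assumed), for which the Wilson upper limit is 0.390.

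- 10/10: Wilson lower limit 0.722. Newcombe lower limit for the difference = 1 − √(0.278² + 0.390²) = +0.52.
- 3/10: Wilson lower limit 0.108. Newcombe lower limit = 0.3 − √(0.192² + 0.390²) = −0.14.

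At that LLOQ the choice of sentence decides whether the comparison with placebo excludes zero. No rates are given for PsVNA, because the documents offer no titer distribution for it. The threshold ratio of L/2 applies there too.

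**The case against.** The strongest reply is that SAP 4.3.2 already contains the right rule. Its first two sentences are complete and agree with SAP 1.2.5.2, SAP 4.3.3 uses the titer scale, and a ratio set against a titer is visibly a slip. This stands as a point about intent. A reader might infer that the SAP has fixed the threshold at LLOQ². The documents do not support that: the section contradicts itself, and how it would be programmed is unknown. SAP 8.1 says the low-value rules came from two memoranda that are not in the documents. It does not make the sentence harmless, because that sentence is the one addressed specifically to low baselines.

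Four further limits also stand.

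- A reader might conclude that the rule decides nearly every subject's status. Exclusion 14 makes a large share likely, but it rests on history and potential contact, no Marburg serology is scheduled at screening, and no share is stated. SAP 4.3.3 plans to tabulate it.
- A reader might think seroconverters would no longer be a subset of seroresponders. For any LLOQ of at least 1, LLOQ² ≥ LLOQ, so the subset relation holds. Only the intended 4-fold against 2-fold spacing is lost.
- SAP 1.2.5.2 splits baselines into above and below LLOQ, which seems to leave a baseline equal to LLOQ unclassified. The general fold rule in SAP 4.3.2 and 4.3.3 covers that case, so the gap is confined to the parameter list.
- Seroconversion is a secondary endpoint. The interim analysis also reports GMTs, reverse cumulative distribution curves and safety. The GMTs and curves do not use this threshold, so a badly discordant seroconversion rate would probably be noticed beside them.

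**Conclusion.** The point holds as an internal contradiction in a responder definition. The third sentence of SAP 4.3.2 is wrong as written, and it conflicts with the two sentences before it and with SAP 1.2.5.2. The algebra needs no assumption: the thresholds differ by a factor of LLOQ/2.

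The practical effect cannot be fixed from the documents. It is nil at LLOQ 2, about one percentage point at LLOQ 10, and severe at LLOQ 50 and above. Those percentages rest on an assumed LLOQ, a lognormal titer, the plan's borrowed geometric SD, and a GMT from a different vaccine. They show how sensitive the endpoint could be and do not forecast this trial's results. The documents do not show that responders will in fact be misclassified. They show that the rule to be programmed is ambiguous for an endpoint reported at the dose-guiding interim analysis.

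**What to change.** Replace the third sentence of the seroconversion paragraph in SAP 4.3.2 with wording such as: *Where the baseline is below LLOQ (or below LOD for ELISA), a subject has seroconverted when the post-baseline titer reaches at least 2 × LLOQ, i.e. 4 × LLOQ/2.*

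As a minor alignment with SAP 4.3.2 and 4.3.3, change > LLOQ to ≥ LLOQ in the four seroconversion and seroresponse definitions of SAP 1.2.5.2.

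Make both changes before unblinded immunogenicity data are analysed, so that the choice of rule is not post hoc. If the interim programs already exist, confirm that they use 2 × LLOQ.

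The cost is SAP wording and a check of the program. Design, data collection and sample size are unaffected.
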